There is an urgent need for effective, non-opioid treatment to manage pain. Particularly, for those whom pharmacologic pain treatments may be harmful, such as those with substance use disorders, PTSD, and other co-morbid mental health issues. The clinical standards for diagnosing and treating pain is based on an incomplete biological understanding of pain, and there are well documented problems with and inefficacy of the current treatment modalities, including dependence, addiction, and cognitive decline. Traditionally, pain treatment is localized, but to effectively treat pain we need to shift our focus to the underlying mechanisms of pain in the brain. Research shows that only 40-60% of all patients that receive pharmacological treatments for pain have a significant positive outcome [15]. Opioids have varying levels of effectiveness depending on type of pain, underlying etiology, and genetics. One of the main reasons for lack of efficacy is that current pharmacological approaches have limited to no effect on the neural mechanisms underlying pain and, in some cases, may make pain worse. For example, opioids tend to be more effective for acute pain, but can actually worsen chronic pain by inducing central sensitization (hyperalgesia) and hypersensitivity [13-17]. This predominant pharmacologic approach ignores the brain's neuroplasticity and ability for cell-regeneration and fails to consider the individual impacts on brain regions where pathological disorders related to pain are subserved. The use of tDCS, which emits a constant, low intensity current through electrodes placed over the head which modulates neuronal activity, lacks these side effects and has shown promise in promoting neuroplasticity [11-12, 16-18]. The mechanisms of cortical modulation by tDCS may activate certain neuronal networks such as increasing glutamine and glutamate under the stimulation, effects on the μ -opioid receptor, and restoration of the defective intracortical inhibition. Precision medicine is a national priority and using technology to identify and treat differences in disease states should move forward as an alternative to pharmacological treatments [16-18]. TDCS is a non-invasive brain stimulation that uses electrical currents to stimulate specific areas of the brain. A constant, low intensity current passes through two to four electrodes, which can be placed on various locations on the head, to modulate neuronal activity. tDCS can administer anodal and cathodal stimulation to excite (depolarization) or inhibit (hyperpolarization) neuronal activity, respectively. Using low amplitude direct currents applied via scalp electrodes to alter cortical excitability is not a novel concept. This non-pharmacological approach has held promise for decades as a way to treat a plethora of neurological and psychiatric disorders. Although tDCS is not currently FDA approved it is considered a non-significant-risk therapy with no record of serious adverse effects [45,46,55]. Health Canada, the European Union, Israel, Singapore and many other regulatory bodies around the world have approved tDCS for medical treatment applications [44,46]. Although there are many neurostimulation devices available on the market only a few have been cleared recently by the FDA for medical use, including the Fisher Wallace Stimulator which is FDA cleared to treat depression, anxiety and insomnia

IRB Protocol for Human Subjects Research

[47] and Neurostar which is FDA cleared to treat depression [49]. Studies have repeatedly shown clinical benefits of tDCS as a therapy for major depression [16–20], bi-polar disorder [21,22], anxiety [23,24], Parkinson’s Disease [26] TBI [28,29], ADHD [30,31], stroke [32,33] and pain [13,25,34–42,50-54] as well as reduction in opioid use [43,44] with no major side effects.

(References listed at end of Protocol document)

2.0 Lay Summary:

Provide a brief description of the proposed research using terms that someone who is not familiar with the science or discipline can understand.

Pain is a severe and growing problem in the United States with more than 116 million Americans suffering from chronic pain and more than \$635 billion spent annually on pain and its related healthcare costs [1]. Additionally, opioid addiction has become a national crisis with nearly 50,000 deaths every year as a result of opioid-involved overdoses and nearly \$78.5 billion spent annually on opioid misuse and addiction [2–4]. Currently available treatments for pain, namely opioid analgesics, have limited effectiveness and can lead to a significant number of side effects and complications including dependence, pharmacodynamic tolerance, sedation, gastrointestinal issues, respiratory depression, immunosuppression, and hormonal changes [5–7]. Effectively treating pain requires an accurate assessment of pain, however current methods of diagnosing and evaluating pain depend on subjective self-reporting including the use of visual and numerical pain scales [8–10]. The subjective nature of describing pain makes it virtually impossible to quantify and therefore difficult to treat and monitor. To overcome this subjectivity, through a non-invasive neuromodulation technique called transcranial direct current stimulation (tDCS) and deep learning, pain can be measured objectively using electroencephalograph (EEG) to assess and personalize treatment. *The overarching goal of this project is to apply transcranial direct current stimulation (tDCS) as an alternative to opioids for the reduction in chronic pain.* Our long-term goal is to use these data to analyze EEG signals and generate personalized tDCS treatment in real-time.

3.0 Purpose:

Describe the purpose, specific aims, objectives, questions to be answered, hypotheses, and/or primary and secondary study endpoints of the Human Research.

The primary objective of the proposed study is to determine the impact of tDCS on pain in substance use disorder (SUD) subjects. The long-term goal of the study is to address the underlying neurobiological deficiencies caused by SUD and provide a more personalized adjunctive SUD treatment.

***Aim 1:* to compare changes in brain waves during tDCS treatment sessions in the treatment (tDCS) and placebo (sham) arms. This aim will be achieved by capturing EEG readings of the entire brain for subjects in each treatment arm at baseline, during the treatment phase, and at final study visit 1 week post treatment.**

***Aim 2:* to compare changes in self-reported pain perception in the treatment and placebo (sham) arms. We will achieve this aim by comparing the baseline pain perception scales results of subjects in treatment and placebo arms to pain perception scales results on the final day of the treatment and again one week later, enabling investigators to determine any short-term change or durable change to pain.**

***Aim 3:* to compare the safety and tolerability of the tDCS system (tKIWI) versus placebo (sham) in terms of any unwanted side effects or adverse events. We will achieve this aim by monitoring subjects’ vitals during the entire session and evaluating results of a**

IRB Protocol for Human Subjects Research

questionnaire after each treatment session and after the final study visit, enabling us to capture reported discomfort.

Our central hypothesis is that applying transcranial direct current stimulation using the patented tKIWI system will safely reduce self-reported chronic pain with little to no side effects. If this hypothesis is accurate, the next steps are to identify mechanistic biomarkers to improve our understanding and ability to accurately diagnose pain disorders which would facilitate the development of pharmacologic and non-pharmacologic treatment modalities using deep learning architecture built into the tKIWI.

Treatments focus entirely on pharmacological and behavioral approaches without evaluating the brain itself [9,10] even though chronic pain has been shown to be significantly related to brain function [8-11]. This creates significant limitations, such as imprecise treatment modalities, medicine side effects, and decreased treatment adherence due to slow progression and increased patient frustration [12-14]. This predominant approach ignores the brain’s neuroplasticity and ability for cell-regeneration and fails to consider the individual impacts on brain regions.

Expected Endpoint / Outcome Measures: The primary efficacy endpoint in this RCT is chronic pain participants in the treatment arm feel a reduction in symptoms of pain and a self-reported reduction in opioid use, or the desire for opioid use. The primary safety endpoint of this RCT is that after both single and multiple treatments, no participants experience clinically significant side effects or adverse events.

4.0 Funding Information:

Indicate all sources of funding for the project, including gift funds, departmental funds, or other internal funding. For each funder, list the name of the funder, and the institutional proposal number or award number you received from Sponsored Projects. For externally funded projects, the information below should match the Study Funding Sources in [eIRB](#).

 No Funding	
 Federal Funding , including flow-through federal funding (i.e., NIH, NSF, DoD, etc.)	Name of funding source:
	Institutional Proposal or Award Number:
	eDoc # (for multi-site projects):
 Industry Funding	Name of funding source:
	Institutional Proposal or Award Number:
	eDoc #:
 Foundation Funding	Name of funding source:
	Institutional Proposal or Award Number:
 Department Funding	Name of funding source: Career Development Award, UAHS

IRB Protocol for Human Subjects Research

 Gift Funding	Name of funding source:
 Other	Name of funding source:

5.0 Resources Available to Conduct the Human Research:

Describe the resources (facilities, time, emergency resources, etc.) available to recruit, consent, conduct study procedures, and analyze data.

Research will be conducted at the UArizona Comprehensive Pain and Addiction Center in [name] lab room 641 with the full support and funding of Family and Community medicine. The CPAC has all the resources required to fulfill this study. We will hire a research coordinator in addition to the PI and Co-I.

Timeline of Study:

Phase	Milestone	Start/Finish	Tasks Overview
Phase 1 Planning Months 1-6	Finalize Clinical Protocol	Month 1 - 2	
 Work with FDA consultants, [name], study coordinator and other personnel to finalize protocol
	Regulatory Approval	Month 1-2	
 Submit UArizona IRB Submit UAHS Contracts Submit IDE application to the FDA Submit to DOD Human Research Protection Office [HRPO]
	Recruitment strategies meetings	Month 1-3	
 Establish access to patient populations Work with clinical network, local enterprises, and providers Develop marketing material, informed consent etc.
	Finalize tKIWI units and software for clinical trial	Month 3-6	
 Adapt tKIWI software for double blind clinical trial, prepare for data anonymization, HIPAA etc. Manufacture 4+ tKIWI systems in different sizes Prepare for data collection and storage
	Training	Month 6	
 Train Clinical Research Coordinator, Study Coordinator, Research Assistants on administering tKIWI blinded, monitoring vitals, administering questionnaires etc.
Phase 2 Clinical Trial Month 7-20	Recruit Patients	Month 7+	
 Recruit 40 chronic pain patients Informed consent Medical questionnaires/surveys etc.
	Baseline Session and Preparation for data collection	Month 10+	
 Collect baseline EEG readings Create patient profiles, anonymize personal information Randomize treatment assignment Preliminary EEG biomarker analysis

IRB Protocol for Human Subjects Research

	Clinical trial (2 weeks)	Month 11-12	
 Each patient has one daily treatment session (blinded treatment or sham)
	Follow up	Month 12-13	
 Follow up with each patient one week and two weeks after clinical trial
	Statistical analysis	Month 14	
 Statistical analysis of data collected including questionnaires, vital monitoring, EEG etc. Publish findings in an academic journal Transition plan for next phase of clinical trial
	Publish	Month 16	
 Publish findings in an academic journal Present findings internally and at conference Plan for next phase of clinical trial Publish biomarkers data in academic journal
	Transition	Month 17+	
 Prepare and submit R01

6.0 Study Population:

- Select all the categories of participants included in the research:

 Healthy adults	 Non-English-speaking subjects
 Non-healthy adults	 UA staff/faculty
 Children (under 18 years old) *	 UA students
 Pregnant women, neonates, and/or fetuses*	 Banner employees
 Prisoners*	 Refugees
 Native Americans, Alaskan Native, and Indigenous Populations*	 Other – please explain: Adults ages 18-79 with a self-reported history or diagnosis of chronic pain (>3mo)
 Adults unable to consent (i.e., cognitively impaired adults) *	

- For each of the above selected categories, describe the inclusion and exclusion criteria. Indicate age range, gender, and ethnicity.

Inclusion Criteria:

Age: 18-79 years old

Gender: Any

Ethnicity: Any

Chronic pain (\geq 3-months); No current use of nonprescription opioids (\leq 1 month); Able and willing to comply with scheduled visits and other study-related procedures to complete the study; Willing and able to give informed consent.

Exclusion Criteria:

- Diagnosis (as defined by DSM-IV) of: any psychotic disorder (lifetime); eating disorder (current or within the past year); obsessive compulsive disorder (lifetime); mental retardation.

IRB Protocol for Human Subjects Research

- History of drug or alcohol abuse or dependence (as per DSM-IV criteria) within the last 3 months (except nicotine and caffeine).
- Subject is on regular benzodiazepine medication which it is not clinically appropriate to discontinue.
- Subject requires a rapid clinical response due to inanition, psychosis or high suicide risk.
- Neurological disorder or insult, e.g., recent stroke (CVA), which places subject at risk of seizure or neuronal damage with tDCS.
- Subject has metal in the cranium, skull defects, or skin lesions on scalp (cuts, abrasions, rash) at proposed electrode sites.
- Female subject who is pregnant.
- Participants who are not fluent in English will not be included in the trial for safety reasons: a) It is usually not possible to have an interpreter reliably available every weekday for up to 4 weeks and it is not safe to give tDCS to a subject who cannot tell us immediately of any side effects; Note that translation of the proposed ACT activity into English has not been validated and that we cannot be confident that they would be accurately translated and validated.
- Minors
- Older than 79 years old
- last use >24 months
- history of EEG or any electrical implant (i.e. pacemaker)
- history of Parkinson's, diagnosis of bipolar, schizophrenia/schizo-affective d/o, OCD, epilepsy, alzheimers
- taking antipsychotic drugs

One of the exclusion criteria is recent history of drug abuse or dependence (in the last 3 months). This would include prescription or non-prescription. If someone uses an opioid (prescribed or not) and does not meet that exclusion criteria, they are eligible to participate for that criteria. We would request that if possible, they refrain from using an opioid within a 3 hours of their appointment.

- **Describe the total number of subjects to be enrolled locally. If obtaining specimens, specify the maximum number of specimens needed for this project.**

The total number of subjects to be enrolled locally is 40 subjects.

7.0 Recruitment Methods:

- **Select the methods used to recruit individuals.**

 Email	 Screening of the Electronic Medical Record (EMR)
 Face to face	 Social media
 Flyers	 SONA System
 In person presentations	 TV, Radio, Print

IRB Protocol for Human Subjects Research

 Online advertisements	 Other – please explain: Click or tap here to enter text.
 Phone calls	

- **Explain the recruitment process. Describe how potential subjects will be identified, where recruitment will take place, when recruitment will occur, and the methods that will be used to recruit individuals.**

Recruitment Location(s): We plan to recruit participants from clinical settings in Tucson, Arizona, such as the Veterans Affairs Hospital and private clinics and hospitals, private enterprises, such as gyms and health-related facilities (chiropractic offices, yoga/pilates studios). We also plan to recruit participants via local Facebook/Instagram and Twitter.

Recruitment Method(s): Recruitment flyers will be distributed to several health clinics and settings. Additionally, ads will be placed on Facebook and Twitter. At this time, we do not plan to conduct in-person recruitment. The flyers will include a link and QR code to a simple Qualtrics form where the interested person will be able to include their name and contact information. Potential participants will then be contacted to schedule an initial visit.

Site authorizations will be sought for each place we put flyers.

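### The primary objective names substance use disorder subjects, but the trial selects and analyses chronic pain participants; the opioid part of the primary endpoint has no aim or analysis

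*Combined protocol and SAP*

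**What the plan says.** **Objective.** Section 3.0 Purpose: "The primary objective of the proposed study is to determine the impact of tDCS on pain in substance use disorder (SUD) subjects". The next sentence there gives a separate long-term aspiration: "The long-term goal of the study is to address the underlying neurobiological deficiencies caused by SUD". Section 2.0 Lay Summary gives a different one: "Our long-term goal is to use these data to analyze EEG signals and generate personalized tDCS treatment in real-time".

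**Goal, hypothesis and Aim 2.** The overarching goal in 2.0 is to use tDCS "as an alternative to opioids for the reduction in chronic pain". The central hypothesis in 3.0 is that the device "will safely reduce self-reported chronic pain with little to no side effects". Aim 2 is "to compare changes in self-reported pain perception in the treatment and placebo (sham) arms". None of these mentions SUD.

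**Primary efficacy endpoint.** The end of 3.0 begins: "The primary efficacy endpoint in this RCT is chronic pain participants in the treatment arm". It then requires these participants to feel less pain and to report using fewer opioids or wanting them less.

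**Who enters.** Section 6.0 asks for adults aged 18-79 with chronic pain. It excludes drug or alcohol abuse or dependence in the preceding 3 months. A further exclusion line refers to last use more than 24 months ago without naming a substance. The timeline in 5.0 plans for 40 chronic pain patients. Sections 7.0 and 8.0 describe recruitment among people with chronic pain in Tucson, through clinics, hospitals, gyms, studios and social media.

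**What is recorded.** Section 10.0 collects mental health diagnoses, SUD among them, and drug-use history as demographic items. The Clinical Trial Protocol table lists a record of medication over the past 24 hours. Table 2 lists a Pain Medication Use Survey at V0 and V6.

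**Analysis.** The Data Analysis text gives one analysis per aim. The Aim 2 analysis compares pain change within and between arms, with no reference to SUD or opioids.

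**The concern.** The primary objective tells the reader to whom the main result applies. Here it names a population that the eligibility criteria do not define and the analysis does not isolate. The trial could finish exactly as planned with no SUD subjects, and so with no data on its own primary objective. More likely it would enrol an unknown mix, and a result from a general chronic pain sample would be reported against an objective about SUD. The risk is a mislabelled conclusion.

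The endpoint adds a second gap. The objective names pain only, while the primary efficacy endpoint also includes opioid use or desire for opioids, and no aim or analysis takes these up. Correcting only the population in the objective would leave it out of step with the endpoint.

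**Working it through.** The check is mainly textual. The plan's own figure is 20 per group × 2 groups = 40, which is consistent. It cannot be rebuilt from a power formula, because the documents give no alpha, power, effect size or SD.

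**Step 1: population, section by section**

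| Place | Population described |
|---|---|
| 3.0, primary objective | SUD subjects |
| 3.0, primary efficacy endpoint | chronic pain participants |
| 5.0, timeline | 40 chronic pain patients |
| 6.0, category and inclusion | adults 18-79 with chronic pain |
| 6.0, exclusion | abuse or dependence in the preceding 3 months kept out |
| 7.0 and 8.0, recruitment | people with chronic pain in Tucson |
| 10.0, design statement | effect on chronic pain |
| 10.0, randomisation | 1:1 lottery, no SUD stratum stated |
| Data Analysis | treatment versus sham, no SUD restriction, stratum or covariate |

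**Step 2: inclusion items.** Section 6.0 lists age, gender, ethnicity, chronic pain, no current nonprescription opioids, compliance and consent (7 items). Section 8.2 adds English, making 7 + 1 = 8. Gender and ethnicity are open to any, so 8 − 2 = 6 items restrict entry. None of the 6 requires current or past SUD.

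**Step 3: how many SUD subjects the criteria allow.** No criterion requires SUD, so the minimum is 0. A person whose abuse or dependence ended more than 3 months ago is not barred by that exclusion and no cap is set, so the maximum is 40.

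**Step 4: aims and analyses.** Naming SUD: 0 of 3 aims, 0 of 3 analyses. Naming opioid use or desire: 0 of 3 aims, 0 of 3 analyses, although the primary efficacy endpoint includes them.

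**Step 5: what is measured for the opioid part.** Medication use has two sources: the past-24-hour record in the Clinical Trial Protocol table and the Pain Medication Use Survey at V0 and V6. The survey's content is not in the documents. No listed assessment is identified as measuring desire for opioids.

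**Illustration only.** No SUD-only comparison is planned and the documents give no SUD share. The table assumes a share of the 40, an even split between arms, equal SDs, no dropout, a two-sided 5% level and a two-sample t-test. The 95% CI half-width in SD units is t(0.975, 2n−2) × √(2/n); the effect detectable with 80% power comes from the noncentral t.

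| Assumed SUD share | n per arm | Half-width (SD) | Detectable effect (SD) |
|---|---|---|---|
| 100% | 20 | 2.024 × 0.316 = 0.64 | 0.91 |
| 50% | 10 | 2.101 × 0.447 = 0.94 | 1.32 |
| 30% | 6 | 2.228 × 0.577 = 1.29 | 1.80 |
| 20% | 4 | 2.447 × 0.707 = 1.73 | 2.38 |
| 10% | 2 | 4.303 × 1.000 = 4.30 | 5.65 |

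The point does not depend on this table.

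**The case against.** **One stray sentence against a consistent plan.** Goal, hypothesis, endpoint, target, eligibility, source population and design statement all say chronic pain, and Aim 2 and its test are unaffected. Much of this stands: the randomised comparison is sound for the sample enrolled, and the correction changes no data. But the sentence at odds with the rest is the primary objective. It cannot be read as motivation, because the SUD long-term goal is stated separately beside it.

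**The text does point to substance use.** The Background speaks of people for whom drug treatment of pain may be harmful, "such as those with substance use disorders, PTSD, and other co-morbid mental health issues". The site is a pain and addiction centre, and SUD and drug history are recorded. The 3-month exclusion read with the 24-month line could reflect an intended window of earlier use. That reading is possible, and the documents do not settle which population was meant. Even so, the 24-month line names no substance, use is not SUD, and a person who never used has no last use and is not excluded by it. None of this defines an SUD population.

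**Stronger readings that the documents do not support.** A reader might infer that people with SUD are barred altogether. They are not: abuse or dependence that ended more than 3 months ago is not excluded by that criterion, and the diagnosis would be recorded. A reader might infer that the treatment comparison is invalid; it is not. A reader might infer that opioid use goes unmeasured. Medication is recorded in two places, and what is missing is an aim, a stated analysis and any measure of desire. Finally, the subgroup figures might be taken as the size of the defect. They describe an unplanned analysis at assumed shares.

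**Conclusion.** The point holds. The planned comparison answers a question about chronic pain participants and cannot support the population named in the primary objective. Its size is the range the criteria leave open, 0 to 40 SUD subjects out of 40, with no minimum and no planned analysis of them. The opioid component of the primary efficacy endpoint is likewise outside every aim and every analysis, and its desire element has no identified measure. Both conclusions rest on the wording alone and need no assumption about effect size or SUD share. Which population the sponsor intends cannot be determined from the documents. Restating the objective for chronic pain is recommended because the rest of the plan already implements it.

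**What to change.** 1. Restate the primary objective in 3.0 as the effect of tDCS versus sham on self-reported pain in adults aged 18-79 with chronic pain. This matches the population and the Aim 2 analysis already planned.
2. Report SUD diagnosis and drug-use history by arm as baseline descriptors, and make no SUD efficacy claim.
3. In the same amendment, make pain the sole primary efficacy endpoint. List opioid use as a secondary outcome with a stated between-arm comparison using the medication data already collected. Confirm first that those data identify opioids, since the survey's content is not in the documents.
4. For desire for opioids, either name a measure and an analysis or remove it from the endpoint.
5. If the sponsor instead intends an SUD population, reconcile the objective, eligibility, recruitment and analysis sections to it. That includes the 3-month exclusion and the 24-month line with no named substance.

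**Cost.** Items 1 to 3 need a wording amendment and one small added analysis, with no change to sample size, randomisation or the Aim 2 test. Keeping desire under item 4 would add a measure and its analysis. The trial gives up any direct claim about SUD, and opioid use and desire are no longer primary. Item 5 would be a substantive change to eligibility, recruitment and analysis.

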The screening will be in redcap where the potential participant will respond to inclusion and exclusion criteria. If the participant is eligible, they will be emailed or provided the consent and enrolled in the study. They will sign the consent during their first visit where demographic data will also be collected and entered into Qualtrics.

Demographics Collected will include:

- Age
- Sex
- Race/Ethnicity
- City, State, Zip
- Phone
- Email
- First Drug Use
- Most Recent Drug Use
- Preferred/Most commonly used drug
- Mental Health diagnoses (including SUD)

The study will occur in 7 visits over an 11 day-period. (see table 2). At the beginning of each visit, the participants will answer a very brief “Pre-Study Session Update” survey to ensure no changes to eligibility have occurred between visits.

Visit 0 will consist of informed consent review and signature, collection of demographic data, baseline self-report pain using the pain surveys (FACES and VAS), brief cognitive survey (MMSE), and baseline EEG recording.

Visits 1-5 will consist of initial EEG recording, three sessions of ramped up tDCS followed by EEG recording and self report pain surveys. Session 1 will be 5 minutes, session 2 will be 5 minutes, and session 3 will be 10 minutes. Details on mAs are listed under tDCS application. The final post visit (V7), on day 11 will consist of no treatment, but a repeat of the data collected on Visit 0.

The visits will take place in [name] lab, room 645 in the UArizona Life Sciences Building. This laboratory is approximately 600sq/ft in size. All [name]’s labs are located next to each other in the Life Sciences North building (Rms 632, 621, 619, 614, 615, 601). All biohazards are disposed according to institutional guidelines. Through [name], we will also have access to shared laboratories that include a molecular biology laboratory of 1,000 sq. ft, an analytical laboratory of 1500 sq. ft. and a radioligand binding laboratory of 1,000 sq. ft. The laboratories include seating space for students and research personnel.

Clinical Trial Protocol: Baseline V0, Tx V0-5, Post V7 (11 days)	
⇒	Pre-Questionnaire (15 min) 
 ○ Cognitive Eval (MMSE) ○ Rate Pain (VAS & FACES) ○ Record medication, activity, symptomology past 24 hours
⇒	Monitor vitals (5 min) 
 ○ HR, BP, PulseO², respiratory, temp, etc (set up continuous measure) ○ Put on device and log into patient portal
⇒	EEG Recording (5 minutes)

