⇒	Treatment/Sham (20 min max)
⇒	EEG Recording (5 min) 
 ○ Rate pain using VAS & Faces) ○ Record symptoms, side effects, complaints
⇒	Visit 11, 5-day lapse return for EEG and VAS and FACES

IRB Protocol for Human Subjects Research

Table 2. Study Visit Schedule T-Arm and P-Arm	
V0 Baseline Week 1	
 • Consent+Demographics • Cognitive Eval (MMSE) • Rate Pain (VAS & FACES) • Pain Medication Use Survey • EEG (4 min)
V1-5 Week 2	
 • Pre-session survey • Vitals • Rate Pain using VAS and FACES • Pre-EEG (2 min) • tDCS1 - .5mA to .75mA (5 min) → EEG (8 sec) • tDCS2 - .75mA to 1.0mA → EEG (8 sec) • tDCS3 - 1.0mA to 1.75mA (10 min) → EEG (8 sec) • Post-EEG (2 min) • Vitals • Rate Pain using VAS and FACES • Side-Effect Self-Report Survey 
*For the Sham group - the first 1 minute of every tDCS session they receive a negligible current titrated from 0mA up to and not to exceed .5mA to give the impression they are receiving the treatment. The remaining treatment times will be followed by no current.

V6 Final Day 11 Week 3	
 • MMSE • Rate Pain using FACES and VAS • Pain Medication Use Survey • EEG (4 min)

tDCS Application:

EEG: The tKIWI uses sensors placed on specific locations of the head for the EEG reading. The first time the headset is applied, our research staff will do some minor fitting. There are sensors that run along a strap front to back (base of skull to forehead) and another side to side (ear to ear). The device uses the standard 10-20 system for both location and names of the sensors. Flat sensors will be placed on the forehead. The headband should come down about a half inch above the eyebrows in front. Once all sensors are green, they are ready to record EEG data.

The hair and dry skin act as a resistor between the sensor and the skull. The more resistance the lower the amplitude of the measured signal. Normally this resistance which is also referred to as impedance in the literature is in the realm of 10-100K ohms. Ensuring a snug fit and moving the hair will decrease impedance and improve EEG readings.

IRB Protocol for Human Subjects Research

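### Aim 3 relies on a side-effect questionnaire at the final visit, but Table 2 schedules that survey only at the five treatment visits

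*Combined protocol and SAP*

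**What the plan says.** **The promise.** Aim 3 in section 3.0 compares safety and tolerability between arms using vital signs and a "questionnaire after each treatment session and after the final study visit". The primary safety endpoint in the same section is that "after both single and multiple treatments, no participants experience clinically significant side effects or adverse events".

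**The final visit, described three times in section 10.0.**
- The narrative says that it "will consist of no treatment, but a repeat of the data collected on Visit 0".
- The last row of the Clinical Trial Protocol table reads "Visit 11, 5-day lapse return for EEG and VAS and FACES".
- The V6 row of Table 2 lists the MMSE and then "Rate Pain using FACES and VAS • Pain Medication Use Survey • EEG (4 min" (minutes).

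**Where side effects are scheduled.** Table 2 names a Side-Effect Self-Report Survey under V1-5 and nowhere else. The tDCS Application text attaches verbal side-effect reporting to treatment visits. The safety-monitoring answer in section 13.0 places it after the treatment.

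**Text that points the other way.**
- The procedure table is headed "Clinical Trial Protocol: Baseline V0, Tx V0-5, Post V7 (11 days", so it claims to cover baseline and the post-treatment visit. Its Pre-Questionnaire row includes an item on medication, activity and symptoms in the previous 24 hours. A later row includes "Record symptoms, side effects, complaints".
- The narrative also has a survey at every visit: "At the beginning of each visit, the participants will answer a very brief" update form, whose stated purpose is to confirm continued eligibility.
- The timeline in section 5.0 plans contact with each patient one and two weeks after the trial period, without saying what will be asked.

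**Analysis.** Data Analysis gives Aim 3 a chi-square or Fisher exact test. It states no interval or confidence level.

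**The concern.** A coordinator will run visits from Table 2. Followed as written, it gives the side-effect form five times and omits it at the final visit, the only contact that Table 2 schedules after V5. Events that begin after the last session, or that persist from it, could then go unrecorded, although Aim 3 counts on a report at that point. Open-ended recall that was never requested cannot be recovered reliably at analysis.

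A smaller matter concerns reporting. The safety endpoint is expressed as a zero count. With 20 per arm, a zero count carries limited information, and the plan does not say that its uncertainty will be shown.

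**Working it through.** **Step 1. Which visit is meant.** The final visit is called V7 in the narrative, Visit 11 in the procedure table and V6 in Table 2. The protocol gives seven visits in total, and V0 to V6 makes seven, so I read all three labels as the single day-11 visit.

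**Step 2. Is the promised questionnaire scheduled there?**

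| Source | Side-effect item at the final visit? |
|---|---|
| Aim 3 | Yes |
| Table 2, V6 | No |
| Procedure table, return-visit row | No |
| Narrative (repeats Visit 0) | None in the narrative's Visit 0 list; a 24-hour symptom item if the Pre-Questionnaire row applies |
| Procedure table, Pre-Questionnaire row | Symptoms over 24 hours only |
| Procedure table, row after Treatment/Sham | Side effects named, but in a step that follows treatment, and this visit has none |
| Start-of-visit update survey | Described only as an eligibility check |
| tDCS Application; section 13.0 | Tied to treatment |
| Section 5.0 timeline follow-up | Content not stated |

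The Pre-Questionnaire row plausibly does apply to the final visit: it contains the MMSE, which Table 2 gives only at V0 and V6.

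**Step 3. How much of the interval could the 24-hour item cover?** The procedure table gives a five-day lapse; Aims 1 and 2 place the last assessment one week after treatment. One day in five is 1/5 = 20%, leaving 4 days. One day in seven is 1/7 = 14%, leaving 6 days.

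**Step 4. What a zero count can show (secondary).** The plan states no figure to reproduce. Inputs: 20 per group (section 10.0; a ceiling, since recruitment is up to 40). The 95% level is my assumption.

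- Exact upper limit for 0/n, two-sided: 1 − 0.025^(1/n).
  - n = 20: 1 − 0.025^(1/20) = 0.168.
  - n = 40, both arms: 1 − 0.025^(1/40) = 0.088.
  - With assumed dropout: n = 18 gives 0.185; n = 16 gives 0.206.
- One-sided 95%, n = 20: 1 − 0.05^(1/20) = 0.139.
- Chance of 0/20 at an assumed true rate p, (1 − p)^20: 0.95^20 = 0.36 at 5%; 0.90^20 = 0.12 at 10%.
- Two-sided Fisher test against 0/20:
  - 4/20: 2 × C(20,4)/C(40,4) = 2 × 4,845/91,390 = 0.106.
  - 5/20: 2 × C(20,5)/C(40,5) = 2 × 15,504/658,008 = 0.047.
  - Five events against none is therefore the smallest split that reaches p < 0.05.
- Risk difference for 0/20 against 0/20, Newcombe 95% interval: −16.1% to +16.1%.

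**The case against.** The best defence is that the lists are shorthand. The return-visit row also drops the MMSE and the medication survey that Table 2 gives the same visit, so its silence on side effects is weak evidence of a deliberate omission. Aim 3 expressly requires the final-visit questionnaire, and side effects are asked about after every session, including the fifth. The protocol also describes known side effects as minor and transient.

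Much of this stands. It makes the problem an inconsistency in the schedule rather than a decision not to collect. But the schedule is what staff follow, and the only named survey is absent from the visit where Aim 3 needs it.

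A reader might infer that nothing about symptoms is asked at baseline or at the final visit. The documents do not support that, because the Pre-Questionnaire row covers the previous 24 hours and its table is headed to include both visits. What survives is narrower: a 24-hour symptom item is neither the promised questionnaire nor a record of the whole interval since V5. The timeline follow-up does not close the gap either, since its content is unstated and Table 2 shows no contact beyond day 11.

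On the endpoint, it is fair to reply that wide intervals come with any small trial and that nothing in the plan prevents reporting them. I accept that.

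**Conclusion.** The inconsistency between Aim 3 and Table 2 is real and should be corrected before visits are run. Its effect is that side effects over roughly four to six days after the last treatment may not be asked about. This rests on reading the three final-visit labels as one visit and on taking the 24-hour item as applying there. The number of events lost cannot be computed from the documents.

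The interval is a reporting improvement, not the correction of an error. A reader might infer that the plan would declare the device safe on zero events or on a non-significant Fisher test. It does not say so: the zero count is listed as an expected outcome, beside a planned comparison between arms. What can be said is that 0/20 on active stimulation is compatible with a true rate of up to 16.8% (two-sided exact, 95% assumed, all 20 treated). Even 0/40 over both arms allows 8.8%, and only half of those participants receive active treatment.

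A reader might also press the lack of a definition of clinical significance and of a stated blinded classification of events. These are missing details, not contradictions. The trial is double-blind and a physician is assigned to monitor reported side effects, so I do not rest the point on them.

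**What to change.** 1. Add the existing Side-Effect Self-Report Survey to the final visit in Table 2, worded to cover all the time since V5. Bring the narrative, the procedure table's return-visit row and Aim 3 into line, using one label for the visit.
2. In the section 5.0 timeline, state whether the one-week contact is this visit and what, if anything, is asked at two weeks.
3. In Data Analysis, accompany the zero-count endpoint and the Fisher test with the proportion of participants with events in each arm, exact 95% intervals based on the numbers actually treated, and the risk difference with its interval.

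**Cost.** A few minutes of an existing form at an existing visit, plus amended wording. No extra participants or visits are needed. The reporting change is free, though the safety statement will read less favourably than a bare zero.
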